7.8.1.4 FSDS-R

The FSDS-R is a 13-item unidimensional measure of sexual-related distress.

- Total Score $Q1+...+Q13$

For all the above PRO questionnaire, missing items in a multiitem scale will be handled by the following methods: Values will be imputed for missing items by “assuming that the missing items have values equal to the average of those items which are present” for the total score in which at least half the items are completed. The total score will be treated as missing if less than half of the items are completed.

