2.5.2 Sexual Health

Unlike hysterectomy for benign conditions, in which the type of hysterectomy does not appear to affect sexual function [Roovers 2003; Thakar 2002], radical hysterectomy for early-stage cervical cancer is well documented to be associated with negative sexual side effects. In one of the earliest prospective trials, 61 women with stage IA, IB, or IIA disease who underwent radical hysterectomy with or without pelvic radiation took part in a 2-hour interview and completed questionnaires [Schover 1989]. Sexual desire, intercourse frequency, and range of activities decreased by one year post-surgery. Subjective excitement and vaginal lubrication decreased at one year and there were more frequent diagnoses of sexual arousal disorders. Psychological symptoms, however, improved over this period of time. In their long-term examination of QoL symptoms following early-stage cervical cancer using the Sexual Activity Questionnaire [Thirlaway 1996], Greimel and colleagues found that 43.3% of the sample reported not being sexually active, with the leading reasons being absence of a partner and lack of sexual desire [Greimel, 2008]. Among the sexually active group, women receiving surgery/radiation therapy had the lowest rates of sexual frequency compared to the other two treatment groups. Women currently receiving treatment had significantly more Sexual Worry on the QLQ-CX24 compared to the group off-treatment [Greimel 2006], but the groups did not differ on current sexual activity.

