2.5.3 Summary of Quality of Life – Related Hypotheses

Given that evidence of fewer side effects with a less radical procedure may drive women's decisions for treatment, examination of these symptom domains is considered to be of major importance in this trial. We will, therefore, explore three key hypotheses regarding these QoL/sexual health secondary endpoints:

Hypothesis 1: We hypothesize that both groups will experience an increase in bowel and bladder side effects, but that the impact of treatment will be of lesser magnitude, on average, in women managed with simple hysterectomy relative to the radical hysterectomy group. This hypothesis will be tested by using outcomes on the QLQ-CX24 QOL module of the EORTC QLQ-C30 instrument (see below).

Hypothesis 2: We hypothesize that both groups will have an increase in sexual distress, (as measured by the **Female Sexual Distress Scale-Revised, FSDS-R**), and that the radical hysterectomy group will show a greater increase relative to the simple hysterectomy group.

Hypothesis 3: We hypothesize that both groups will show a decrease in overall sexual function (as measured by the **Female Sexual Function Index, FSFI, Total Score**), and that the radical hysterectomy group will show a greater decrease relative to the simple hysterectomy group.

Exploratory hypotheses: We hypothesize that most domains of the FSFI (e.g. desire, arousal, lubrication, orgasm, pain, satisfaction) will decrease in both surgery groups, and that the radical hysterectomy group will show a greater decrease relative to the simple hysterectomy group.

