Sexual activity can include caressing, foreplay, masturbation, and vaginal intercourse.

Sexual intercourse is defined as penile penetration (entry) of the vagina.

Sexual stimulation includes situations like foreplay with a partner, self-stimulation (masturbation), or sexual fantasy.

Sexual desire or interest is a feeling that includes wanting to have a sexual experience, feeling receptive to a partner's sexual initiation, and thinking or fantasizing about having sex.

Sexual arousal is a feeling that includes both physical and mental aspects of sexual excitement. It may include feelings of warmth or tingling in the genitals, lubrication (wetness), or muscle contractions.

Circle only one item per question.

Question	Response options (please circle)
1. Over the past 4 weeks, how satisfied have you been with your overall sexual life?	5 = Very satisfied 4 = Moderately satisfied 3 = About equally satisfied & dissatisfied 2 = Moderately dissatisfied 1 = Very dissatisfied
2. Over the past 4 weeks, how often did you feel sexual desire or interest?	5 = Almost always or always 4 = Most times (more than ½ the time) 3 = Sometimes (about ½ the time) 2 = A few times (less than ½ the time) 1 = Almost never or never
3. Over the past 4 weeks, how would you rate your level (degree) of sexual desire or interest?	5 = Very high 4 = High 3 = Moderate 2 = Low 1 = Very low or none at all

Question

Response options (please circle)

- | | |
|---|---|
| 4. Over the past 4 weeks, did you engage in sexual activity of any kind with a partner and/or by yourself (masturbation)? | 0 = No sexual activity (neither with a partner nor by myself) |
| | 1 = Sexual activity with a partner only |
| | 1 = Sexual activity by myself only |
| | 1 = Sexual activity both with a partner and by myself |

If you selected “0 = No sexual activity (neither with a partner nor by myself)”, please skip remaining questions on this questionnaire. If you selected any other response, please continue.

- | | |
|--|--|
| 5. Over the past 4 weeks, how often did you feel sexually aroused (“turned on”) during sexual activity or intercourse? | X = No sexual activity |
| | 5 = Almost always or always |
| | 4 = Most times (more than ½ the time) |
| | 3 = Sometimes (about ½ the time) |
| | 2 = A few times (less than ½ the time) |
| | 1 = Almost never or never |

- | | |
|--|-----------------------------|

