| 6. Over the past 4 weeks, how would you rate your level of sexual arousal (“turned on”) during sexual activity or intercourse? | X = No sexual activity |
| | 5 = Very high |
| | 4 = High |
| | 3 = Moderate |
| | 2 = Low |
| | 1 = Very low or none at all |

- | | |
|--|-------------------------------|
| 7. Over the past 4 weeks how confident were you about becoming sexually aroused during sexual activity or intercourse? | X = No sexual activity |
| | 5 = Very high confidence |
| | 4 = High confidence |
| | 3 = Moderate confidence |
| | 2 = Low confidence |
| | 1 = Very low or no confidence |

- | | |
|---|--|
| 8. Over the past 4 weeks, how often have you been satisfied with your sexual arousal (excitement) during sexual activity or intercourse? | X = No sexual activity |
| | 5 = Almost always or always |
| | 4 = Most times (more than ½ the time) |
| | 3 = Sometimes (about ½ the time) |
| | 2 = A few times (less than ½ the time) |
| | 1 = Almost never or never |

- | | |
|---|--|
| 9. Over the past 4 weeks, how often did you become lubricated (“wet”) during sexual activity or intercourse? | X = No sexual activity |
| | 5 = Almost always or always |
| | 4 = Most times (more than ½ the time) |
| | 3 = Sometimes (about ½ the time) |
| | 2 = A few times (less than ½ the time) |
| | 1 = Almost never or never |

Question	Response options (please circle)
10. Over the past 4 weeks, how difficult was it for you to become lubricated (“wet”) during sexual activity or intercourse?	X = No sexual activity 1 = Extremely difficult or impossible 2 = Very difficult 3 = Difficult 4 = Slightly difficult 5 = Not difficult
11. Over the past 4 weeks, how often did you maintain your lubrication (“wetness”) during sexual activity or intercourse?	X = No sexual activity 5 = Almost always or always 4 = Most times (more than ½ the time) 3 = Sometimes (about ½ the time) 2 = A few times (less than ½ the time) 1 = Almost never or never
12. Over the past 4 weeks, how difficult was it to maintain your lubrication (“wetness”) during sexual activity or intercourse?	X = No sexual activity 1 = Extremely difficult or impossible 2 = Very difficult 3 = Difficult 4 = Slightly difficult 5 = Not difficult

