7.8.1.3 FSFI

The FSFI is a 19-item self-report measure of female sexual function that provides scores on six domains of sexual function (desire, arousal, lubrication, orgasm, satisfaction and pain) as well as a total score:

- Desire $(Q1+Q2) * 0.6$
- Arousal $(Q3+...+Q6) * 0.3$
- Lubrication $(Q7+...+Q10) * 0.3$
- Orgasm $(Q11+...+Q13) * 0.4$
- Satisfaction $(Q14+...+Q16) * 0.4$
- Pain $(Q17+...+Q19) * 0.4$
- Total Score $(Q1+...+Q19) / 19 * 1.2$

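### The FSFI total is missing by rule for women not sexually active at a visit, so Hypothesis 3 is tested only among women active both at baseline and at that visit

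*SAP*

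**What the plan says.** **Form.** The FSFI in Protocol Appendix VI has 20 items. Item 4 asks about sexual activity in the past four weeks. A woman who reports none is told: "please skip remaining questions on this questionnaire". Several later items also offer the option "X = No sexual activity". Neither document gives that code a value.

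**Scoring.** SAP 7.8.1.3 begins: "The FSFI is a 19-item self-report measure of female sexual function". Its formulas run from Q1 to Q19. The missing-item rule is in SAP 7.8.1.4, but its scope is general: "For all the above PRO questionnaire, missing items in a multiitem scale will be handled by the following methods". If at least half the items are answered, the rest take the mean of those answered. Otherwise: "The total score will be treated as missing if less than half of the items are completed".

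**Analysis.** SAP 7.8.4 compares change from baseline by Wilcoxon test at each visit and by a linear mixed model over time.

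**Hypothesis.** Hypothesis 3 in Protocol 2.5.3 concerns the FSFI total. It expects that "both groups will show a decrease in overall sexual function", with the larger fall after radical hysterectomy.

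**Background.** In a long-term cohort cited in Protocol 2.5.2, "43.3% of the sample reported not being sexually active". The leading reasons given are having no partner and lack of desire.

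**The concern.** Sexual activity at a follow-up visit is a state observed after randomization and surgery. The protocol itself names lack of desire as one leading reason for inactivity. A woman whose function falls until she stops sexual activity therefore has no FSFI total at the visits where her outcome is worst. The arms are then compared within a group defined partly by the outcome, and randomization no longer protects that contrast. If more women become inactive in one arm, a real difference in function could be masked. Fewer women would also contribute than Protocol 14.6 assumes.

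Compliance will not reveal this. SAP 7.8.3 counts a questionnaire as received once a single question is answered, so these women count as compliant.

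**Working it through.** **1. The plan's own figure.** Inputs from Protocol 14.6 and Table 1 (Protocol 2.5.4): difference 5, SD 21 (Table 1 assigns this SD to the FSFI), 80% power, two-sided 0.05, 1:1 allocation.

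n per arm = 2 × (1.960 + 0.842)² × 21² / 5² = 277, or 554 in total (556 with the t distribution). The stated 560 reproduces, and power at 560 is 80.4%.

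**2. Items answered by an inactive woman.** She completes items 1 to 4.
- By content, item 1 is satisfaction, items 2 and 3 are desire, and item 4 is the activity screener, which is not one of the 19 scored items. That gives 3/19 = 15.8%.
- By the SAP's literal numbering, Q4 counts as an item: 4/19 = 21.1%.
- Half of 19 is 9.5, so at least 10 answers are needed. The total is missing under both readings.

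**3. Domains, by item content.** Desire 2/2 (scored); satisfaction 1/3; arousal 0/4; lubrication 0/4; orgasm 0/3; pain 0/3. Only desire survives. Under literal numbering, arousal (Q3 to Q6) would have 2 of 4 answers and might be filled in from a desire item and the screener.

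**4. Who enters the comparison.** A change score needs a total at baseline and at the visit. A woman inactive at baseline, for example after her diagnostic procedure, has no change score at any visit. The instruction to recall an earlier active period at baseline is printed on the FSDS-R, not in the FSFI text. A woman active at baseline drops out only at her inactive visits.

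**5. Whether the analyses repair this.** The Wilcoxon test uses observed change scores only. The mixed model keeps a woman's active visits, but it is valid only if missingness depends on observed data. Inactivity caused by current, unrecorded function does not meet that condition.

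**6. Women with a total.** The inactive share in this trial is unknown, so a range is assumed, with all 700 women responding. Scored = 700 × (1 − share); power = Φ(5√N/(2 × 21) − 1.96).

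| Assumed inactive | Women with a total | Power |
|---|---|---|
| 20% | 560 | 80% |
| 30% | 490 | 75% |
| 43.3% (cited cohort) | 397 | 66% |
| 50% | 350 | 61% |

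With the 750 randomized according to SAP 2.1, 43.3% inactive leaves 425 women and 69% power. For a given share, these counts are upper limits: the sexual health questionnaire is optional and a change score needs activity twice.

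**7. Scale.** The SAP's total is the sum of 19 items divided by 19, times 1.2. With items scored 1 to 5 it runs from 1.2 to 6. No change can exceed 4.8, so a 5-point difference cannot occur on it. The powers above describe the protocol's assumptions, not the SAP's score.

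**8. Illustration with assumed values only.** Take true mean changes of −5 and −10, SD 21, and a common activity threshold. Let the correlation between change and the tendency to stay active be 0.3, 0.6 or 1.0. With 43.3% inactive overall, the 5-point difference becomes 4.7, 3.9 or 2.0 among active women. With 20% inactive it becomes 4.8, 4.2 or 2.9.

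**The case against.** **Activity is analysed elsewhere.** QLQ-CX24 item 49 asks every respondent about sexual activity. SAP 7.8.1.2 scores it, and Table 44 compares change by arm at each visit. The CX24 is also not an optional component in the way the sexual health questionnaire is. A reader might infer that an arm difference in inactivity would go unseen; item 49 shows that it need not. This part of the objection stands. But the SAP does not link item 49 to the reading of the FSFI, and it does not change who is in the FSFI contrast.

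**The FSFI is not the lead measure.** Protocol 2.5.4 makes sexual distress the primary outcome within sexual health, and the FSDS-R has no activity skip. This stands and limits the damage, but the FSDS-R answers Hypothesis 2, not Hypothesis 3.

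**A differential effect is not shown.** In a small prospective comparison cited in Protocol 2.5.2, all women resumed intercourse after either operation. The same section says frequency is a poor indicator of sexual response. The 43.3% comes from women 7.3 to 9.7 years after diagnosis, some of them irradiated, while this trial assesses 3 to 36 months. This stands: direction and size are open. A reader might infer that the FSFI result could reverse. Nothing in the documents supports that, and the illustration only shrinks the difference.

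**Scoring may follow a published algorithm.** Protocol 14.6 refers to other published algorithms. The SAP writes out its own formulas and missing-item rule, however, and a woman who follows the skip instruction leaves the items blank in any case.

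**Conclusion.** The concern holds for the FSFI total, which is the Hypothesis 3 endpoint, and by item content for five of the six domains. It follows from the form's skip instruction and the SAP's half-of-items rule and needs no assumption about the inactive share.

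It should not be read as saying that the whole FSFI excludes inactive women: desire is still scored, and the restriction applies visit by visit. Nor is 66% power a finding. It rests on one external figure, and at 20% inactive the planned 560 is still reached with 700 full responders. Whether a difference would in fact be masked depends on arm-specific inactivity, which the documents do not give. As written, the FSFI total can describe women active at both times. It cannot support a statement about all randomized women.

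**What to change.** In SAP 7.8.4:

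- Report and compare the proportion sexually active (FSFI item 4, read with QLQ-CX24 item 49) by randomized arm and visit, beside the FSFI results.
- Label the FSFI total and the non-desire domains as 'among sexually active women'.
- Add a sensitivity Wilcoxon test in which women active at baseline and inactive at the visit receive the worst rank.

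To make these workable, SAP 7.8.1.3 should also map its item numbers to the 20-item form and say how the no-activity code is handled.

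**Cost.** No new data are needed, only a few table rows and one further test per visit. The drawback is that some inactivity, such as having no partner, is unrelated to surgery. The worst-rank result is therefore a sensitivity analysis only.

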7.8.2 Data Sets

The analyses of PRO data will be restricted to treated patients who have completed at least one PRO questionnaire.

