12.1 Therapy After Protocol Treatment

The management of patients who complete protocol treatment (or who never undergo protocol treatment) is left to the discretion of the Investigator. The visit schedule for those patients who receive other anti-cancer therapy should not be modified as endpoints will be assessed for as long as the patient can be followed and an intent-to-treat analysis will be performed.

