14.2 Primary Endpoints and Analysis

Pelvic recurrence rate at 3 years, the primary endpoint of this study, will be estimated by the Kaplan-Meier estimate for the 1-probability of pelvic relapse-free survival (PRFS) at 3 years, where the PRFS is defined as the time from randomization to the time when any documented evidence of recurrence within the pelvic field (see Sections 10.0-10.3). Patients who relapsed outside of the pelvic field or died before the documentation of pelvic relapse will be censored at the time of first documented extra pelvic relapse or death. If the patient is alive without any relapse at the time of final analysis, PRFS will be censored on the date of the last disease assessment. All patients will be included in the analyses in the arms to which they are randomized regardless of whether they receive the assigned treatment (intention-to-treat). Upper limit of a one-sided 95% confidence interval for the difference in the pelvic recurrence rates at 3 years between simple hysterectomy to radical hysterectomy will be calculated based on the Greenwood estimate for the variance of the estimated 3 year PRFS and non-inferiority of simple hysterectomy to radical hysterectomy will be claimed when this upper limit is lower than or equal to 4%. A “per-protocol” sensitivity analysis based on only eligible patients who have received any study treatment and analyzed based on arms they are treated will also be performed for non-inferiority testing.

The experience of PRFS, a secondary endpoint of the study, will be described by the Kaplan-Meier method for all randomized patients in both treatment groups on the base of intention-to-treat. Based on Jung *et al.* (sample size computation for two-sample non-inferiority log-rank test, [Jung, 2005]), non-inferiority of simple hysterectomy to radical hysterectomy will be claimed when the upper limit of a one-sided 95% confidence interval for the hazard ratio of simple hysterectomy to radical hysterectomy, derived from a stratified Cox model adjusting for stratification factors at randomization and with a single treatment covariate, is lower than or equal to 2.04. The non-inferiority margin 2.04 for hazard ratio is corresponding to a margin of 4% for the 3 year PRFS between simple hysterectomy and radical hysterectomy when the 3-year PRFS in radical hysterectomy was estimated at 96%. A “per-protocol” sensitivity analysis will also be performed.

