14.6 Analysis for Quality of Life

The quality of life and sexual health of patients in this study will be assessed by respectively EORTC QLQ-C30 core questionnaire with its module QLQ-CX24, the Female Sexual Function Index (FSFI), and the Female Sexual Distress Scale (FSDS-R). The EORTC QLQ-C30 and QLQ-CX24 are self-administered cancer specific questionnaires with multi-dimensional scales. QLQ-C30 consists of both multi-item scales and single item measures, including five functional domains, a global quality of life domain, three symptom domains, and six single items, while QLQ-CX24 has three multi-item subscales: symptom experience, body Image, and sexual/vaginal functioning, and five single items pertaining to menopausal symptoms, lymphedema, lower back pain, tingling and numbness, and sexual enjoyment. FSFI is a 19-item self-report measure of female sexual function that provides scores on six domains of sexual function (desire, arousal, lubrication, orgasm, satisfaction, and pain) as well as a total score. The FSDS-R is a 13-item unidimensional measure of sexually-related distress. Scoring of the quality of life and sexual health data will be completed following the procedures recommended by the EORTC Study Group on Quality of Life and other published algorithms.

The quality of life and sexual health data will be analyzed to look for statistically and clinically significant differences between two treatment arms. Questionnaire compliance rates will first be ascertained for each group at each measurement time point. Mean scores at baseline and the change scores from baseline at each follow-up assessment time point will be calculated for each subscale and summary scores and compared between two arms by Wilcoxon test. The profile of change scores over time between two treatment arms will be compared using linear mixed models.

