4.3 Safety

The safety endpoints are serious and non-serious adverse events, other safety events during the surgeries and follow-up.

5. Sample Size and Power

It was estimated that 3-year pelvic recurrence rate for the radical hysterectomy is around 4% and the non-inferiority of the simple hysterectomy to radical hysterectomy would be claimed if its 3-year pelvic recurrence rate is 8% or lower. In the original protocol with pelvic relapse free survival (PRFS) as the primary endpoint, this is equivalent to claim the non-inferiority of the simple hysterectomy to radical hysterectomy when a hazard ratio in PRFS of simple hysterectomy to radical hysterectomy is less than or equal to 2.04. In order to conclude the non-inferiority at 0.05 level with 80% power when PRFS is the same in the two arms, a total of 49 pelvic relapses would be required before the final analysis is performed. Assuming that enrollment rate is 200 patients/year and all patients would be followed for additional 3.5 years after the last patient randomized, enrollment of 700 patients in 3.5 years was required to observe the required number of pelvic relapses at the time of final analysis.

With 350 patients enrolled in each arm, the study would have 85% power to conclude the non-inferiority based on a margin of 4% in the revised primary endpoint, i.e., 3-year pelvic recurrence rate, at $\alpha=0.05$ when the pelvic recurrence rate at 3 years is assumed the same in the two arms.

6. Data Set Descriptions

Three types of analysis samples will be used:

Intention-to-treat Patients:

All patients who have been randomized in the study with the treatment arm being as randomized.

Per-protocol Patients:

All eligible patients who have received hysterectomy, except those who were found to have more advanced stages of cervical cancer on sentinel node mapping, pelvic node dissection or other intraoperative findings consistent with pelvic disease, with the treatment arm being as actually treated.

All Treated Patients:

All patients who have been have received hysterectomy with the treatment arm being as actually treated.

7. Statistical Analysis

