7.4 Treatment Information

All treated patients as defined in Section 6 will be included in the analysis based on the type of surgery received by the patients.

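### The patient-reported outcome analyses are limited to treated patients, on the natural reading grouped by operation received, and no as-randomized analysis is specified.

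*SAP*

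**What the plan says.** SAP 7.8.2 sets one population for every PRO analysis: "The analyses of PRO data will be restricted to treated patients who have completed at least one PRO questionnaire". It does not cite SAP Section 6, and the shells for Tables 42 to 45 carry no dataset line.

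SAP Section 6 defines three sets. Only one is named for treatment received, All Treated Patients: "All patients who have been have received hysterectomy with the treatment arm being as actually treated". SAP 7.4 uses it in that sense: "All treated patients as defined in Section 6 will be included in the analysis based on the type of surgery received by the patients". SAP 7.6 uses it for safety. The intention-to-treat set is also defined: "All patients who have been randomized in the study with the treatment arm being as randomized". Section 7.8 does not use it.

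SAP 4.2 places PROs among the secondary efficacy endpoints. SAP 7.5.3 to 7.5.7 and the table shells analyse the others on that list by intention to treat: the relapse endpoints, survival, and the node, parametrial and margin rates.

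The protocol applies intention to treat to the primary endpoint: "All patients will be included in the analyses in the arms to which they are randomized regardless of whether they receive the assigned treatment". Its Section 12.1 adds that "endpoints will be assessed for as long as the patient can be followed and an intent-to-treat analysis will be performed". Section 14.2 gives an explicit as-treated rule for adverse events. Section 14.6 says PRO data will be "analyzed to look for statistically and clinically significant differences between two treatment arms" but names no population and no as-treated rule.

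**The concern.** The PRO comparisons are two-sided tests of whether simple hysterectomy does less harm (Protocol 2.5.3 and 14.6). If non-inferiority is shown, they become a main argument for adopting the smaller operation. Randomization protects such a comparison only if women stay in their allocated arm and are not removed because of what happened afterwards.

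The SAP set permits both departures. A woman allocated to one operation who has the other is counted with the other arm. A woman with no hysterectomy is left out. Protocol 8.1 allows surgery to be abandoned when spread is found, Section 12.0 allows the patient to decline, and the trial is not blinded (Section 4.0). Such departures can be related to disease extent or to preference, and so to later symptom and sexual-health scores.

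**Working it through.** **Planning figures.** Protocol 14.6 gives SDs of 13.5, 10 and 21 for change scores, differences of 7, 5 and 5 points, 80% power and two-sided 0.05. It prints FSDS-R for both the second and third scales; Table 1 in Protocol 2.5.4 shows that SD 21 belongs to the FSFI. With 1:1 allocation, total N = 4 × (1.960 + 0.842)² × (SD/difference)², rounded up per arm.

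| Scale | SD | Difference | N, normal | N, t-test | N stated |
|---|---|---|---|---|---|
| CX24 symptom | 13.5 | 7 | 118 | 120 | 120 |
| FSDS-R | 10 | 5 | 126 | 128 | 130 |
| FSFI | 21 | 5 | 554 | 556 | 560 |

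The stated totals are reproduced, so the planning figures are a sound yardstick.

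**Bias from regrouping by operation received.** The documents give no crossover rate, so these inputs are assumptions: equal arms, no true effect, a share c of the simple arm has radical surgery, and women of that type change by g SD for the worse whichever operation they have. Randomization puts the same share c of such women in the radical arm, where they receive their allocated operation. Let m be the mean change in all other women.

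- As randomized, both arms average m + c·g·SD, so the difference is zero.
- As treated, the simple group averages m.
- As treated, the radical group averages [(m + c·g·SD) + c(m + g·SD)]/(1 + c) = m + 2c·g·SD/(1 + c).

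The spurious advantage for simple hysterectomy is 2c·g·SD/(1 + c).

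| Scale (target) | c = 2%, g = 0.5 | c = 5%, g = 1 | c = 10%, g = 1 |
|---|---|---|---|
| CX24 symptom (7) | 0.26 | 1.29 | 2.45 |
| FSDS-R (5) | 0.20 | 0.95 | 1.82 |
| FSFI (5) | 0.41 | 2.00 | 3.82 |

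At c = 3% on CX24: 2 × 0.03 × 0.5 × 13.5/1.03 = 0.39 points for g = 0.5, and 0.79 for g = 1. That is 6% to 11% of the 7-point target. At c = 1% the range is 0.13 to 0.27. If crossover ran from radical to simple in similar women, the sign would reverse by symmetry.

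**Power cost of analysing as randomized.** Suppose 2%, 5% or 10% of the effect is lost to crossover or non-receipt, so the difference is multiplied by 0.98, 0.95 or 0.90. The totals needed become 122, 130 or 146 for CX24; 132, 140 or 156 for FSDS-R; and 578, 614 or 684 for FSFI. If all 700 women contributed scores, power would exceed 99% for the first two scales and be 87%, 85% or 81% for FSFI. These powers are upper bounds, because the sexual health questionnaires are optional (Protocol Section 6.0).

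**Whether the data exist.** For women who had the other operation, questionnaires were scheduled as usual. For women without hysterectomy the protocol is inconsistent. Section 9.0 defines an end-of-treatment date for them and times questionnaires from that date. Appendix I, footnote 1, puts them on the after-recurrence column, where the questionnaire row is empty. Separately, SAP 7.8.3 bases compliance on living women required to complete the assessment, a denominator not limited to treated women, so compliance and analysis would describe different groups.

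**The case against.** **The arm rule is inferred.** Section 7.8.2 does not cite Section 6, whereas 7.4 and 7.6 do. It could mean women who had surgery, analysed by randomized arm. That stands as an uncertainty, and the bias figures depend on it. Even on that reading, women without hysterectomy are still dropped after randomization.

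**The protocol does not plainly forbid the set.** Section 14.6 is silent on population, and the intention-to-treat sentence in 12.1 sits in a paragraph about keeping the visit schedule. A reader might infer a direct contradiction between protocol and SAP; the text does not go that far. The firmer argument is the SAP's treatment of every other endpoint in 4.2, together with the protocol's explicit as-treated rule for adverse events and the absence of one for PROs.

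**Imbalance and direction are not shown.** A reader might infer that departures differ by arm and favour simple hysterectomy. Nothing in the documents describes conversion from simple to radical surgery or shows that such women fare worse. Pelvic node dissection is common to both arms (Protocol 8.2), and abandonment follows nodal or extrauterine findings (8.1), which gives no reason to expect imbalance from that source. Crossover could run either way.

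**Larger illustrations are not supported.** An excess of 20 points at 3% crossover would give about 1.2 points, 17% of the CX24 target. But 20 points is about 1.5 SD, and twice the 10-point change Table 1 expects after radical surgery. The formula also concerns means; the Wilcoxon tests at each visit are less sensitive to a few extreme scores, although the mixed model is mean-based.

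**Some women may contribute no follow-up scores under any rule.** If Appendix I governs, women without hysterectomy have baseline data only. SAP 7.5.1 also counts pelvic disease found at surgery as a relapse on that date, while SAP 7.8 schedules PROs before first pelvic recurrence. If that rule carries over, these women leave the scheduled assessments whatever the analysis set. This limits what can be recovered for them, but does not affect restoring the randomized arm for women who had the other operation.

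**Conclusion.** The point holds as a weakness in the specified analysis set. It does not show that bias occurred. As written, and on the natural reading of 7.8.2, the PRO comparison moves women between arms according to surgery received, drops those without hysterectomy, and has no as-randomized counterpart.

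The size is conditional. With 2% to 10% simple-to-radical crossover and an excess of 0.5 to 1 SD unrelated to the operation, the bias toward simple hysterectomy is about 0.3 to 2.5 points on CX24, 0.2 to 1.8 on FSDS-R and 0.4 to 3.8 on FSFI. If departures are rare, the effect is small; SAP Tables 1 and 6 will show how many there were. The change is worth making because these comparisons carry the benefit claim and the remedy is cheap.

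**What to change.** - In SAP 7.8.2, make the main PRO analysis all randomized patients with available PRO data, in the arm to which they were randomized. Do not require both a baseline and a follow-up questionnaire for entry to the set, which would be a stricter filter than the SAP's own.
- Keep the as-treated set as a sensitivity analysis, citing Section 6 for its definition.
- Name the dataset in Tables 42 to 45.
- Report by randomized arm how many women lack follow-up PROs because they had no hysterectomy, and state whether the intraoperative-relapse rule of SAP 7.5.1 ends their scheduled PRO assessments.
- Reconcile Protocol Section 9.0 with Appendix I, footnote 1, on PRO collection in women without hysterectomy.

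The cost is a short text edit and one extra run of the PRO tables. No new data are needed for women who had the other operation. For women without hysterectomy, follow-up PRO data may be missing, and that should be reported.
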